16. IDENTIFICATION PROCEDURES, SECURITY AND THERAPEUTIC ADHERENCE OF THE INVESTIGATION SUBJECTS

16.1 Recruitment

The subject will be recruited in the ophthalmologic consultation of the participating research centers, in which a goal of scrutinized and randomized subjects are contemplated according to their scrutiny and recruitment capacity.

16.2 Subject identification

All the subject of the study will be identified through a number and their initials.

In the scrutiny stage a number will be assigned to the participant in a consecutive manner, employing 3 digits and once included the subject will be assigned with the subject's number (CFR number) which will be conformed of 3 digits of the molecule, 2 of the center's number, and 3 digits of the consecutive number assigned at the research center.

For example:

155/01/001 (molecule number/ center's number/ subject's number at the center).

16.3 Subject discontinuation

The following are the reasons why a subject may leave the study prematurely:

Subject's decision. The subject that desires to leave the study for any reason is allowed to do so at any moment, but they must inform the researcher. In all cases, the researcher must try to establish contact with the subject as soon as possible for a final evaluation with the purpose of:

Documenting the subject's decision in clinical notes, obtaining the motive/s of the departure and writing them down in the exit format of the CRF, evaluate the clinical state of the subject, take timely therapeutic measures if required: handling of an adverse event or concomitant illness.

Researcher's decision. Especially if adverse events occur and the researcher considers that this can risk the subject's health, the indications in the adverse events section must be followed, or if an important disease occurs that needs medical prescription incompatible with the objective of the study. It will be reported in the clinical notes and a reporting format of the serious adverse events will be filled and the Ethics committee will be informed, clinical monitor and pharmacovigilance of Laboratorios Sophia.

An erroneous inclusion according to the protocol. The decision on whether the subject will remain in the study will be made conjunctly by the researcher and the sponsor.

Other motives (insufficient response, need of another treatment)

In all the cases, the available data will be kept for the security analysis (intention-to-treat population)

16.4 Research products recall

In case of research products recall (decided by the competent authorities of the sponsor) the sponsor will immediately inform the researcher.

The researcher in collaboration with the sponsor's representatives (clinical monitor) must with haste:

- ❖ Interrupt the supply of the affected research products to the subjects.
- ❖ Inform the involved subjects that they must stop the application of these research products immediately and take them to the center.
- ❖ The monitor will organize the return in order to carry on with the destruction of the study drug, both the used as the not used to Laboratorios Sophia S.A. de C.V., according to procedures.

16.5 Adherence to the treatment

Compliance of the administration of the study drugs by the subjects will be evaluated at the facilities of Laboratorios Sophia once the dropper bottle of each subject are returned by the researcher. Each bottle will be weighed in an analytical balance and the difference with respect to the initial weight of the bottle; all values above 70% will be considered as adequate adherence to the treatment with respect to the posology described in the present protocol for Zebesten® and the buyer. It will also be evaluated in the research center by the researching physician

In the event that the adherence to the study drug is under 70 %, it will be considered that the results obtained from the participant are analyzed by intention to treat, see the section for the statistical analysis.

17. ADVERSE EVENTS

17.1 Adverse event, definition and communication

17.1.1 Overview

Adverse events (EA) may appear during the study, these may be associated or not with the study drug. If at any time any of the subjects may present any adverse event classified as serious that is derived from the drug's administration, the guidelines of the Official Mexican Norm 220 SSA1 2012 Installation and Operation of the Pharmacovigilance shall apply. The administration of the drug will be interrupted and the administration of an alternative therapy will be prescribed, as per the judgement of the main researcher.

An adverse event is any medical occurrence in a subject or subjects of a medical research, to whom a pharmaceutical product was administered and that does not necessarily have a causal relation with this treatment. Therefore. An EA can be any unfavorable and unintended sign (including an abnormal laboratory finding), symptom or disease temporally associated with the use of a medicinal (research) product, whether it is or not related to this.

The researcher must report the adverse events occurred during the study from the moment in which the subject signs the informed consent to be included in the clinical trial until the conclusion of the last procedure described in the approved version of the study protocol.

In all cases the etiology must be identified as far as possible and the sponsor must be notified. An “unexpected adverse event” is understood as any EA that is not identified in the nature, severity or frequency in the Researcher’s Manual or in the information of the risks described in this protocol.

17.2 Classification and severity

17.2.1 Classification

The adverse events are divided in two categories according to their importance: “serious” and “not serious”, this classification determines the procedures that must be used to report and document the adverse event.

A **serious adverse event** is that which:

- ❖ Threatens the life or causes the death of the subject.
- ❖ Makes it necessary to hospitalize or prolong the hospital stay
- ❖ It is the cause for persistent or meaningful incapacity
- ❖ It is the cause of alterations or malformations in the newly born

A non-serious adverse event is that which does not comply with any of the previous criteria.

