4. JUSTIFICATION

Steroids are considered the “golden standard” for treating inflammation and may cause multiple adverse events such as: increase in intraocular pressure, susceptibility to infection, delay in the healing of corneal injuries, glaucoma, and posterior subcapsular cataracts, among others; for which reason AINEs represent a safer alternative for the treatment of long-term post-surgery inflammation.

Most AINEs are weak acids and are ionized with the tear pH, limiting their permeability towards the anionic cornea. Due to their pharmacological characteristics, AINES must be combined with insoluble cationically-charged complexes, as is the case with benzalkonium chloride, to facilitate their penetration and solubility.

Currently, four topical non-steroid anti-inflammatories are approved by the Food and Drug Administration (FDA) for the treatment of inflammation: diclofenac 0.1 %, ketorolac 0.5 %, nepafenac 0.1 %, and bromfenac 0.09 %. Of these, bromfenac is the only one approved at a dosage of twice a day and which is currently used to treat post-surgery inflammation, blepharitis, conjunctivitis, and escleritis.³

The use of topical ocular AINES was limited to their chronic use, which also presents adverse events such as corneal abrasion, tear film dysfunction, or even corneal melting. Recent evidence regarding bromfenac being used for 3 weeks indicates that its dosage of twice a day appears to be safe for the ocular surface.

There is a report by Frucht J, et al. which compares the use of indomethacin 0.1 % versus dexamethasone 0.1 % to handle ocular signs and symptoms associated with Pterygium and Pinguecula, under a dosing schedule of 1 drop 6 times a day for 3 days, followed by 1 drop 4 times a day for 11 days for both drug products.

Although the authors assert that both drug products are efficient and safe, the dosing schedule entails the frequent administration of the drug products, which represents an increase in the risk of the subject's failure to follow the treatment, for which reason we propose bromfenac as a useful drug in the control of clinical signs such as hyperemia in an inflammatory disease model that requires a drug with less adverse events and a lower frequency of administration than other AINES.⁴

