History of autoimmune diseases that potentially can present ocular manifestations, like: rheumatoid arthritis, juvenile rheumatoid arthritis, Sjögren syndrome, seronegative spondyloarthropathies, Systemic lupus erythematosus, multiple sclerosis, arthritis of giant cells, Graves' disease, among others.

Infectious diseases

Ophthalmologic diseases that can potentially require treatment in the following 3 months.

Ocular surgical procedures (in the last 3 months)

Diseases in the previous segment that require treatment or endanger the visual prognosis (posterior uveitis, diabetic retinopathy, macular degeneration, etc.)

History of penetrating corneal transplantation.

History of scarring inflammatory diseases such as Steven-Johnson syndrome, pemphigus etc.

History of ocular allergic reaction and/or adnexa.

12.2.3 Elimination criteria of the subject included in the study:

1. Corneal damage clinically perceptible or evidenced in the staining of the surface (lissamine green and fluorescence) for example:

(a) Corneal de-epithelisation grade V (according to the Oxford scale)

(b) Corneal Melting.

(c) Corneal Dellen.

2. Added ocular surface diseases that require a treatment different to Zebesten ® or added treatments that are indicated for the new diagnostic.

3 Opacities in ocular transparent mediums (cornea, clear, vitreous body) that prevents the assessment of the anterior chamber or the following segment.

4. The subject's own decision.

5. Unable to keep the follow-up appointments.

6. Added not authorized treatment or self-medicated

7. Herbal treatments that affect the course of the disease or that produce other complications not related to the disease.

8. Systematic diseases that require immunomodulatory treatment or biologics that affect each line of the inflammatory cascade.

9. Retinal diseases secondary to chronic-degenerative diseases that require treatment to preserve the function and/or anatomy.

10. Inflammatory retinal diseases

11. Installation of uveitic picture in any ocular uveal level.

12. Uveitic picture that mean an ophthalmologic emergency that requires immediate treatment.

13. Ocular diseases that require surgical treatment.

14. Ocular diseases that require intravitreal injections.

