17.3 Report of non-serious adverse events

The reports of adverse events classified as “non-serious” must be reported in the specific section of the case report form of the clinical protocol, as per what is indicated in the guide for the filling of the case report form.

During each monitoring visit, the correct filling of the non-serious adverse event report in the specific section of the case report form will be verified. It must be assured that before base closure of the study the non-serious adverse events are completed with a final resolution of adverse events and the totality of the information requested in the form of case report.

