17.5.6 Reporte de los Eventos Adversos Serios

An active search of EAs must be performed using the spontaneous reports of the subject and physical explorations and interviews performed by the researcher during the visits.

If the EA ends up interrupting the study, the researcher must complete the FCR, in the section corresponding to Termination of the study, and specify if the event is serious or not.

A form of serious adverse events must be completed by the main researcher or the physician in charge and sent to the sponsor within the 24 hours following the notification; even if not all the required information is yet available at the moment. All the information gathered afterwards must be sent immediately once it is available. The researcher must provide an adequate and complete follow-up of the EAs. At any time they must provide an updated report of the EAs and report in writing when there is a final result for it.

In the same manner, all the EAs must be reported to the Committees of Ethics in Research, as well as the Regulatory authorities.

All the EAs as per the previous definitions and independently of the treatment or relationship with the study drug must be notified as soon as the event is known.

The researcher must notify the sponsor of the event sending the form "Serious Adverse Event Report" ("first notice") within the 24 hours after knowing about it via email with all the available information on the serious adverse event to the department of Pharmacovigilance of Laboratorios Sophia, S.A. de C.V as well as attaching a copy by email to the monitor in charge of the center.

17.5.7 Pharmacovigilance responsible:

[name] [name].

Email: [contact]

Laboratorios Sophia, S.A. de C.V.

[name]

[name]

[name]

[contact] (Direct)

[name]

[contact]

Direct assistance line, toll-free number: [name]

Non-serious adverse events (mild and moderate) are reported to the regulatory authority by the end of the study (after the report or in the report) and the serious adverse events immediately.

18. MONITORING AND AUDITING PROCEDURES.

Each research center as well as each researcher will have a clinical monitor assigned and authorized to revise, monitor and procure the information obtained from the study subjects.

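### The serious-event definition has no medically important or sight-threatening category, so a corneal melt can be non-serious by rule, and sections 16.3 and 17.5 give reporting instructions that do not agree with it

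*Combined protocol and SAP*

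**What the plan says.** Section 17.2.1 states that the serious/non-serious class fixes how an event is reported and documented. It lists four criteria for serious, the first being "Threatens the life or causes the death of the subject". The others are hospitalisation or a longer stay, incapacity that is persistent or meaningful, and alterations or malformations in a newborn. The remainder is closed off by rule: "A non-serious adverse event is that which does not comply with any of the previous criteria".

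The protocol foresees corneal harm. Section 4 says that chronic use of topical ocular NSAIDs presents "adverse events such as corneal abrasion, tear film dysfunction, or even corneal melting". Section 12.2.3 makes "Corneal damage clinically perceptible or evidenced in the staining of the surface" the first ground for eliminating a subject, with Oxford grade V de-epithelisation, melting and dellen as examples. No section says how these events are to be classed.

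The reporting instructions are in four places:

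- **17.3:** non-serious events "must be reported in the specific section of the case report form of the clinical protocol".
- **16.3,** withdrawal by the researcher's decision: "a reporting format of the serious adverse events will be filled", with notice to the ethics committee, the monitor and pharmacovigilance.
- **17.5.6:** the serious-event form goes to the sponsor within 24 hours. The section also says "all the EAs must be reported to the Committees of Ethics in Research, as well as the Regulatory authorities", and that events are to be notified as soon as they are known. For an event that ends participation, the researcher completes the termination section and states whether the event is serious.
- **The sentence that closes 17.5, after the contact block of 17.5.7:** "Non-serious adverse events (mild and moderate) are reported to the regulatory authority by the end of the study", and serious ones immediately.

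Under section 7.3, the researcher may consult the sealed codes at the centre for a serious adverse event, once the sponsor authorises it.

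**The concern.** In a trial of an ocular NSAID, the harms that matter most threaten the eye rather than life, and they are often managed without admission. A definition built only on death, hospitalisation, incapacity and newborn harm can leave such an event non-serious at the time it is found, before any lasting loss is known. Because the class controls the expedited notice and access to the codes, the gap decides who hears of the event and when.

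The instructions elsewhere do not close the gap consistently. Two centres could each follow the text and file different forms for the same corneal event. Evaluation of the corneal and conjunctival epithelium is part of specific objective 2, so this concerns the safety question the trial sets itself.

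**Working it through.** There is no stated figure to reproduce. The check follows one event through each section, then uses calendar arithmetic to size the delay.

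**Test event:** a corneal melt managed without admission and without persistent or meaningful incapacity.

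1. *17.2.1.* Not a threat to life, no admission, no qualifying incapacity, no newborn harm. None of the four criteria is met, so it is non-serious.
2. *17.3.* It is entered in the case report form. This route covers every non-serious event, whatever its intensity.
3. *Closing sentence of 17.5.* It is due at the authority by study end if mild or moderate. Section 17.2.2 also has a severe grade. For a severe event that is non-serious, the timing to the authority is not stated. The parenthesis treats intensity as if it were seriousness.
4. *17.5.6, committee and authority sentences.* Read literally, the event goes to the ethics committees and authorities as soon as known, which contradicts step 3. If serious events are meant, there is no contradiction, but the test event is not covered.
5. *16.3.* If the researcher withdraws the subject because the event can risk health, or because of an important disease that needs incompatible medication, a serious-event form is required with no test of seriousness. Section 17.5.6 expects the researcher to say whether a withdrawal event is serious, so it allows for non-serious ones. The two do not agree.
6. *7.3 and 17.1.1.* Code access is tied to a serious event. The Mexican pharmacovigilance norm is invoked only for an event already classified as serious and derived from the drug. Neither reaches the test event.

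**Delay to the authority under step 3.** Inputs: enrolment of 6 months (section 12), taken as 183 days, or 183 / 6 = 30.5 days per month; last contact at day 36 ± 2 (section 11.4). Assumption: study end is the last subject's day-36 call.

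- Last subject enters on calendar day 183. The call falls on 183 + 35 = day 218.
- First subject, event on study day 7: 218 − 7 = 211 days (209 to 213 with the call window), and 211 / 30.5 = 6.9 months.
- Subject enrolled on calendar day 30, event on study day 7, which is calendar day 36: 218 − 36 = 182 days, or 182 / 30.5 = 6.0 months.
- Last subject, event on study day 21: 36 − 21 = 15 days.

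The delay is thus about 6 to 7 months for an early subject and about two weeks for the last. The protocol also allows the report to the authority to come in or after the study report, which could lengthen both.

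**The case against.** The strongest reply is that a melt already has an early route. It is an elimination criterion, the subject would leave the study, and the health-risk wording of 16.3 fits. That section calls for the serious-event form, and 17.5.6 puts that form on the 24-hour path. This stands in part: a melt handled under 16.3 would be notified early. But 16.3 also says that the adverse-event section must be followed, and that section classes the same event as non-serious. The early route depends on which instruction a centre obeys.

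The sponsor would also not be left unaware. Section 17.1.1 requires sponsor notification in all cases, section 18 requires electronic entry within 72 hours of the visit, and 17.3 has entries checked at monitoring visits. This stands, and it confines the delay to the authority and, where 16.3 is not triggered, the ethics committee.

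Four stronger readings are tempting, and the documents do not support them:

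- *That a melt can reach the authority only at study end.* Under 16.3, or under 17.5.6 read literally, there is an earlier instruction. A melt causing admission or qualifying incapacity is already serious.
- *That 17.5.6 plainly contradicts itself.* Its general sentences sit under an untranslated heading about serious events and lead into the serious-event form, so serious events were probably meant.
- *That every mild event leading to withdrawal generates a serious-event form.* Section 16.3 is tied to risk to health or an important disease.
- *That a severe non-serious event has no route at all.* Section 17.3 gives it one; only the timing to the authority is missing.

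**Conclusion.** The point holds as a gap in the definition together with instructions that must be reconciled. A corneal event that threatens sight but meets none of the four criteria is non-serious by rule, outside the 24-hour notice and the code-break provision. Sections 16.3, 17.2.1, 17.3 and 17.5 do not give one consistent path for it.

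The size is a possible delay of about 6 to 7 months to the authority for an early subject, resting on the assumptions that study end is the last day-36 call and that enrolment takes the planned 6 months. The defect itself does not depend on that figure.

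A reader might infer that the primary outcome is compromised. It is not: the table in 13.3 counts adverse events as a number of cases, whatever their class, and filing a form does not change an event's class under 17.2.1. Sample size and efficacy analysis are untouched. This should be fixed because it concerns timely safety reporting of a foreseeable harm.

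**What to change.** - **17.2.1:** add a fifth criterion for an important medical event that expressly includes sight-threatening events. Give corneal melting as an example, and have the investigator assess the other corneal events in item 1 of 12.2.3 against it. Sending dellen or every grade V defect automatically by the 24-hour route would go further than the documents support, since no section calls these serious or sight-threatening.
- **16.3:** replace the automatic serious-event form with an instruction to classify the event under 17.2.1 and use the form that matches.
- **17.5.6:** write serious adverse events in full wherever the 24-hour notice and the committee and authority routes are meant.
- **Closing sentence of 17.5:** delete the parenthesis on mild and moderate, so that the route depends on seriousness alone and severe non-serious events have a stated timing. Define end of study.

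The cost is protocol wording, site training and a few more expedited reports. No visits, procedures or subjects are added.

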17.2.2 Severity of the Adverse Events

The grade of severity of the adverse events must be evaluated by the researcher in charge or the person delegated for such task, as per the intensity of the clinical manifestations.

- ❖ **Mild intensity** is considered for those adverse events that do not interfere with everyday activities; these that may or may not require the suspension of the drug’s administration.
- ❖ **Moderate intensity** is considered for those adverse events that interfere with everyday activities; (may provoke sick leave at work or school), but do not directly threaten the subject’s life, they may or not require the suspension of the drug’s administration.

- ❖ **Severe intensity** is considered for those adverse events that prevent the subject from performing their everyday activities.

